## View: SF - Research Determination

## Research Determination

**1. \* Select one of the following that applies to the project**

- Research Project or Clinical Investigation**
- Exception from Informed Consent for Planned Emergency Research
- Humanitarian Use of Device for Treatment or Diagnosis
- Humanitarian Use of Device for Clinical Investigation
- Emergency Use of Investigational Drug, Biologic or Device
- Treatment Use (Expanded Access to Investigational Product for Treatment Use)
- Center or Institute Administrative Grant Review

ID: HM20005575

View: SF - Federal Regulation

## Federal Regulations

1. \* Is this a Clinical Trial:

Yes  
 No

2. Is this an Applicable Clinical Trial that must be registered and reported to [clinicaltrials.gov](http://clinicaltrials.gov):

Yes  
 No

3. \* Is this a FDA regulated study:

Yes  
 No

4. \* Is this study supported by the Department of Defense (DoD):

Yes  
 No

5. \* Check if any of the following funding sources apply to this research:

---

None of the above

View SE\_Banner

ID: HM20005575

## View: SF - Conflict of Interest

## Conflict of Interest

1. \* To the best of your knowledge, do you (as PI) or any other engaged individual hold a financial conflict of interest related to this study?

- Yes
- No

**2. If Yes, provide:**

- Name(s) of the engaged conflicted individual(s)
- Brief description of the financial conflict of interests

3. \* Describe any potential non-financial conflicts of interest for members of the research team that could impact the conduct of the study (if None, please state "None"):

the S  
None

4. Describe any institutional conflict of interest with this research that you or any member of the research team may be aware of.

None

ID: HM20005575

View: SF - Communication Plan for Research Team

## Communication Plan for Research Team

1. \* Describe the process that will be used to ensure that all persons at all involved sites assisting with the research are adequately informed about the protocol and their research related duties and functions:

Investigators will brief and inform clinical personnel of study design by poster in break room, email and personal interactions before first enrollment; however, clinical personnel will be not be performing any research related duties. Members of the research team will meet after each subject to review protocol, data acquisition and to go over any problems identified.

## IRB Panel Setup

1. \* To which IRB is this study being submitted for review:

VCU IRB

Western IRB

NCI Central IRB

Other IRB (Request to Defer to Another Institution)

## Review Setup

1. \* Does this study involve greater than minimal risk:

Yes  No

2. \* Review Type Requested: (subject to IRB approval)

Full Board

Expedited

Exempt

## Research Description

1. \* Describe the study hypothesis and/or research questions. Use lay language whenever possible.

We hypothesize that in very low birth weight infants who require respiratory support via noninvasive ventilation, that synchronizing the ventilator breath with the baby's breath using neurally adjusted ventilatory assist (NAVA) will reduce the number and/or severity of apnea/bradycardia/desaturation episodes compared to nasal intermittent positive pressure ventilation (NIPPV).

2. \* Describe the study's specific aims or goals. Use lay language whenever possible.

The specific goal is to measure the number and severity of cessation of breath/low heart rate/low blood oxygen level events (ie, apnea/bradycardia/desaturation events) in a 4 hour period while receiving one of the two types of non-invasive ventilation modes (either NIPPV or NAVA) currently used in very low birthweight infants.

3. \* Describe the study's background and significance, including citations, or upload a citation list in document upload. Use lay language whenever possible.

Very low birthweight (VLBW) premature infants in the NICU frequently require respiratory support for prolonged periods of time. Invasive mechanical ventilation (which requires intubating the baby with a tube to provide breaths) can lead to ventilator-induced lung injury. Because of this, noninvasive respiratory support has become increasingly popular, as this form of ventilation has been shown to reduce the incidence of permanent lung injury. (1)

There are several methods to provide non-invasive support. The gentlest is continual flow of air and oxygen via nasal cannula. However, premature infants often develop apnea, either because the signals from their immature brain are not yet sufficient or because the muscles in the back of their throat do not get enough nerve signals to maintain sufficient opening. As a result, babies on nasal cannula often develop clinical apnea/bradycardia/desaturations. Before putting these babies back on invasive ventilation, clinicians often try to provide the baby with machine breaths while still on non-invasive ventilation. This method is called nasal intermittent positive pressure ventilation and studies have demonstrated that this method reduces the need for re-intubation in VLBW infants (1) and reduces the rate of apneic events.

A newer method of non-invasive breathing support that has been FDA approved and used in VLBW infants, synchronizes the machine generated breath with the patient's own breath. Neurally adjusted ventilatory assist (NAVA) does this by replacing the standard nasogastric tube with a nasogastric tube that has sensors which detect the baby's natural diaphragm activity, which signal the ventilator to breath in synchronization with the baby. Studies have shown that the efficacy of nasal ventilation is significantly enhanced when the machine breath is synchronized with the patient breath (2). Synchronization also reduces diaphragmatic dysfunction (3). It can improve gas delivery, reduce work of breathing, and make patients demonstrably more comfortable (4).

Neurally Adjusted Ventilatory Assist (NAVA) is a mode of partial support. NAVA can be used both in intubated patients (invasive NAVA) as well as in extubated patients who require noninvasive positive pressure ventilation (noninvasive NAVA) (5). Invasive NAVA has been shown to deliver equivalent ventilation while requiring lower peak inspiratory pressure, as well as reduced respiratory muscle load, compared to conventional pressure support ventilation.

Currently, the choice of using NIPPV or NAVA is at the clinician's discretion. Both are regularly and frequently used in the VCU Health System's NICU. There are no studies that have examined whether NAVA triggered synchronized ventilation is more effective than non-synchronized NIPPV. In addition, there is limited data on the synchronicity and mechanics of non-invasive NAVA in VLBW infants. Information comparing clinical and lung mechanical outcomes between NIPPV and NIV NAVA would significantly benefit VLBW care providers and, consequently, their patients in getting the best evidenced-based therapy.


5. Moerer O, Beck J, Brander L, Costa R, Quintel M, Slutsky AS, et al. Subject-ventilator synchrony during neural versus pneumatically triggered non-invasive

**4. \* Briefly describe the study design, including all interventions or interactions with research participants and access to identifiable data. Use lay language whenever possible.**

STUDY DESIGN

a. Subjects

Subjects: VLBW (< 1501 grams birthweight) infants in the VCU Health System NICU who are receiving either NPPV or non-invasive NAVA therapy as ordered by their clinical providers. Investigators are clinicians who work in the NICU and will therefore be able to identify eligible subjects.

NAVA and NIPPV are different modes for the way non-invasive ventilation breaths are triggered. Both utilize the same delivery system, ventilator, cannula, etc. In NIPPV, the ventilator breaths are triggered by time, i.e. the ventilator sends a breath to match the prescribed rate like one every 3 seconds for a rate of 20 breaths per minute, no matter whether the patient is inhaling or exhaling. In NAVA, the normal feeding tube is replaced by a special tube that has a sensor located around where the diaphragm surrounds the esophagus. The sensor picks up the electrical signal of the diaphragm muscle contracting, and this mark of the beginning of inhalation is used to trigger a machine breath, so the machine and the patient are coordinated. Aside from the catheter connection, all other procedures are the same.

b). Randomization - the order of modes will be assigned based on a random number table using a 5 block design to match the DSMB reporting needs. c) The change from one mode to the next involves activating a switch on the ventilator. There are no procedures that need to be done to the subject. They will remain in their current environment, connected to all the routine and study-related monitoring equipment. d) During the study, which involves both modes, the subjects will be monitored as routine by the staff, as well as one of the study faculty ([name] or [name]). In the event that one of us needs to step away briefly, an attending neonatologist and a neonatal fellow are on site in the NICU

As part of routine care, infants on either mode have a nasogastric tube in place. Those subjects who are receiving NIPPV will have their nasogastric tubes replaced by a NAVA nasogastric tube. The subject will then be randomized to one of the two modes (NIPPV or non-invasive NAVA). After a one hour stabilization period, during which small adjustments to the non-invasive settings can be made to clinically optimize the settings, the study will begin. A Nellcor pulse oximeter probe will be placed on an extremity to provide a continuous non-invasive downloadable measure of saturation (blood oxygen level) and heart rate. Data from the ventilator will be downloaded in real-time to a laptop. These data will be recorded for 4 hours continuously. After that, the ventilator will be switched to the other mode (NIPPV to NAVA or NAVA to NIPPV), at the same PEEP and respiratory rate. Again, one hour will be allowed to adjust the ventilator settings. Data will then be collected for 4 hours on the second ventilation mode. At that time, the clinician will be informed if either mode was significantly better and the clinician will decide which mode the patient will return to. We will not know which mode is better until the data are analyzed in aggregate. We're concerned about safety perspective where the subject is on Mode A as chosen by the clinician, and we find that during the time they are on Mode A, they have far more events than when we have them on Mode B. This would be valuable information, since the choice of NPIIV vs. NAVA is currently not clearly indicated. To address this, we will provide the clinician with the results that are available at the time of the study. This will be number of events that are routinely measured clinically, i.e. events that cause alarms such as apnea or bradycardia or desaturations outside the clinical limits. These are objective measures that the clinician can incorporate into their decision making if they so choose.

Data to be collected will include heart rate, saturations from the pulse oximeter, and respiratory rate, expired tidal volume, peak pressure and synchronization from the ventilator.

Clinical data will include: birthweight, gestational age, age at study (days of life) and pre-study ventilator settings. Data will be kept in a secure HIPAA compliant database and only study investigators will have access to it.

Analysis: The simultaneous recordings will be scored for: a) Apnea (cessation of breath resulting in no airflow for > 20 seconds or for > 5 seconds if accompanied by bradycardia [HR < 100 bpm] or desaturation [Oximetry < 85%]) b) Bradycardia (hr < 100 bpm for > 5 seconds) c) Desaturation (< 85% for > 5 seconds) d) Synchronicity, measured as average triggering and cycling-off delays for each modality, and total wasted patient respiratory efforts for each modality.

Primary outcome: The number of isolated apneas, bradycardias and desaturations and the number of combined events will be compared by mode of ventilation.

Secondary outcome: a) Synchronicity from the ventilator at the time of an event. This will be analyzed to determine whether asynchronicity is related to increased number of events during the study. b) Overall asynchronicity counts will be determined by ventilator data that can be uploaded and analyzed with software supplied by the manufacturer. c) average mean airway pressure and peak inspiratory pressures required in each mode of ventilation.

There are no well-characterized tools to measure premature infant 'comfort'. There are semi-subjective pain scores that the nursing staff use but we are more likely to have irritation or discomfort from the probe. Thus, this will be an ongoing assessment of a) the infant's state - quiet sleep, quiet awake, agitated, restless, etc. b) new onset tachycardia or tachypnea coincident with applying the probes. c) facial grimaces that are different than baseline as assessed by the nurse caring for the patient

The threshold for an adverse event will be dependent on the baseline level. If the baseline rate is, say, 4-6 events an hour, a 25% increase is 1 event, which is within the patient's variance. On the other hand, in one having no events, just one event is a 100% increase. We have 2 criteria - 1) An event that requires intervention with breathing support such as with more breaths or a bag and mask, 2) an increase from baseline of at least 4-5 events/hr. from baseline

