## Study Population

1. \* Provide the total number of participants you expect to enroll in this study under the VCU IRB:  
15

2. If this is a multi-Center Project, what is the total anticipated number of subjects across all sites:

3. \* Provide justification for the sample size:

Sample Size

Based on published data, monitored events occur at an average frequency of 9.2 over a 4-hour period. The degree of variability is not known but assuming an SD of 50%, a sample size of 10 subjects would have an 0.8 power for a 50% reduction in events at an alpha of 0.05. A similar study to ours comparing NIPPV and flow-synchronized NIPPV (2) had 19 participants and achieved statistically significant differences between the two modalities. Based on this, we are anticipating a need for 15 subjects

4. \* List the study inclusion criteria:

1. < 1501 grams (VLBW infant)
2. Patient must be receiving daily caffeine therapy for apnea
3. On non-invasive ventilation, either NIPPV or non-invasive NAVA

5. \* List the study exclusion criteria:

1. No concerns for acute sepsis (i.e., blood cultures, if drawn, have been negative for 48 hours, and no active signs/symptoms of sepsis).
2. No history of meningitis or seizures
3. No signs of increased intracranial pressure, including bulging fontanelle, presence of ventricular shunt device, or ventriculomegaly by most recent ultrasound.
4. Presence of Grade III or IV intraventricular hemorrhage
5. No cyanotic heart defects or clinically significant congenital heart disease. Will allow PDA, PFO, and mild to moderate ASD/VSD as determined by pediatric cardiology.
6. Non-English speaking legal representatives (parents)

6. \* Check all participant groups that are likely to be involved in this study. If it is possible that a regulated vulnerable population (children, pregnant women, prisoners) COULD BE involved in the study, be sure to check them:

Healthy Volunteers

Children

Emancipated Minors

Pregnant Women

Fetuses, Neonates, Fetal Material or In-Vitro Fertilization

Prisoners

Decisionally Impaired Adults

When cancer is integral to the research - cancer Patients, Family Members, Healthcare Providers or Prevention

VCU Health System Patients

Non-VCU Patients

VCU/VCUHS Students or Trainees

VCU/VCUHS Employees

Individuals with Limited English Proficiency

Active Military Personnel

When researching in a K-12 environment - populations Within School Districts or Other Learning Environments

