## DSMP Details

1. \* Describe your Data Safety Monitoring Plan for monitoring the data collected to ensure the safety of participants:

At 5 subject intervals, data on the number of failures, and the frequency/severity of events will be provided to [name], MD, MPH who is Chair of Neonatal Medicine at VCU. She will assess the study for safety. Her opinion about whether the study should continue is final.

The DSMP is the chief of the service. We will submit outcomes and adverse event data to her after every 5 subjects. It is an expectation that the DSMP assessment of whether to stop or continue will be made in writing to the PI within 28 days, and a copy will be forwarded to the other investigators, the device sponsor and the IRB each time.

ID: HM20005575

[View: SF - Consent Qualifiers](#)

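### Blocks of five cannot balance two mode orders, and with no period term in the comparison a first-to-second-period drift can leak into the mode difference.

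*Combined protocol and SAP*

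**What the plan says.** Research Description, item 4, describes a two-period crossover. Each infant is recorded for 4 hours on one mode, and then "the ventilator will be switched to the other mode (NIPPV to NAVA or NAVA to NIPPV), at the same PEEP and respiratory rate". After one hour of adjustment a second 4-hour recording follows. There are therefore two orders: NAVA first or NIPPV first.

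On allocation, the same item says "the order of modes will be assigned based on a random number table using a 5 block design to match the DSMB reporting needs". It gives no allocation ratio, no composition within a block, no rule for the odd slot and no method of concealment.

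DSMP Details, item 1, explains the five: "At 5 subject intervals, data on the number of failures, and the frequency/severity of events will be provided". Study Population, item 3, sets the size: "Based on this, we are anticipating a need for 15 subjects".

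The primary outcome paragraph in Research Description, item 4, compares event counts between the modes. It names no test or model and no term for period or sequence.

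**The concern.** Blocking the order in a crossover serves to put each mode first equally often, so that whatever changes between the two recordings cancels out of the mode comparison. A block of five cannot do that for two orders. The reason given, alignment with the safety reports, does not require it, because a report can be sent after any five infants whatever the block size.

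The second recording starts about 5 hours after the first (4 hours of recording plus 1 hour of adjustment). If event rates shift over that time, an unadjusted comparison with unequal orders credits part of the shift to one mode. The analysis as written has nothing to take it out. At stake are the size of the estimated mode effect in a 15-infant trial and some of its power.

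**Working it through.** **Inputs from the documents.** Two orders and a block of five (Research Description, item 4, read with DSMP Details, item 1). N = 15 (Study Population, item 3). From the same item, "monitored events occur at an average frequency of 9.2 over a 4-hour period", an SD of 50% (0.5 × 9.2 = 4.6), a 50% reduction (4.6 events), alpha 0.05, and power 0.8 with 10 subjects.

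**Assumed input.** The drift π is the change in events per 4 hours from the first to the second recording. The documents give no figure, so a range is used: 1, 2 and 4.6 events, and 10%, 25% and 50% of 9.2 (0.92, 2.3 and 4.6).

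**Step 1. The plan's own power figure.** A two-sided paired t-test with difference 4.6, SD of the within-infant difference 4.6 and n = 10 has power 0.803. This reproduces the stated 0.8, provided the 50% SD is read as the SD of the difference. On the same inputs, power at n = 15 is 0.949.

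**Step 2. Order splits.** If each block is 3:2 with random direction, three blocks have 2³ = 8 equally likely patterns.
- All three lean the same way in 2 of 8: 9:6, probability 0.25.
- Otherwise, 6 of 8: 8:7, probability 0.75.
- If the same order takes the third slot in every block: always 9:6.

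**Step 3. Leak into the mode difference.** An infant's mode difference is the true effect plus π in one order and minus π in the other. The unadjusted mean is therefore shifted by π × (n₁ − n₂)/N.
- 8:7: 1/15 = 6.7% of π.
- 9:6: 3/15 = 20% of π.

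| Assumed drift (events per 4 h) | Leak at 8:7 | Leak at 9:6 |
|---|---|---|
| 0.92 | 0.06 | 0.18 |
| 1 | 0.07 | 0.20 |
| 2 | 0.13 | 0.40 |
| 2.3 | 0.15 | 0.46 |
| 4.6 | 0.31 | 0.92 |

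The target effect is 4.6 events.

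**Step 4. Effect on the test.** Simulation with 200,000 runs per case, SD of the difference 4.6, true effect 4.6, and the leak opposing the effect. Power:

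| Drift | Unadjusted, 8:7 | Unadjusted, 9:6 | Period-adjusted, 9:6 |
|---|---|---|---|
| 0 | 0.949 | 0.949 | 0.939 |
| 0.92 | 0.938 | 0.926 | 0.938 |
| 2.3 | 0.895 | 0.847 | 0.938 |
| 4.6 | 0.696 | 0.530 | 0.938 |

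With no true effect and a non-zero drift, the unadjusted test rejected in 0.008 to 0.048 of runs at these two splits. Type I error is not inflated, because an ignored drift also widens the SD. That widening costs power even when the orders are nearly equal, as the 8:7 column shows.

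**Step 5. Adding period.** Averaging the two order-specific mean differences cancels π exactly at any split. Efficiency relative to equal orders is 4n₁n₂/N²: 4 × 9 × 6/225 = 0.96 at 9:6 and 4 × 8 × 7/225 = 0.996 at 8:7.

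**Step 6. Even blocks.** With balanced blocks of 2 and 4, the fifteenth infant is the first of a block or the third of a block of 4. Either way the excess is exactly one, so 15 infants always split 8:7.

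**The case against.** The strongest reply is that the block size matters little. An odd total of 15 cannot do better than 8:7, and random-direction blocks of five already reach that three times in four. In the remaining quarter, even blocks save 0.20 − 0.067 = 0.133 of the drift: 0.13 or 0.27 events for drifts of 1 or 2, against a standard error near 4.6/√15 = 1.19. If the odd slot is random, the expected bias over all possible lists is zero. The severe power loss needs a drift of half the baseline rate, a 9:6 split and an opposing direction together. A period term removes the bias whatever the blocks. All of this stands, and it is why the block change should be paired with the period term. It does not defend the plan as written, which has neither and will be analysed on one realised list.

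A reader might infer more than the documents support:

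- That any time trend leaks. A calendar trend between infants cancels, because each infant is its own control. Only a change from the first to the second recording leaks.
- That every safety report is unbalanced, and that even blocks would cure this. The plan does not say whether reports are cumulative. If they are, random-direction 3:2 blocks give 5:5 at infant 10 with probability 0.50. The first report is 3:2 or worse under any scheme, because five is odd.
- That the imbalance would distort the decision to continue. DSMP Details describes failures and event frequency and severity, not a table of mean mode differences.
- That knowing the block lets investigators steer treatment. If the 3:2 direction is random, the fifth assignment is determined in 40% of blocks, and always if the composition is fixed and known. Every infant receives both modes, so foreknowledge affects only order and timing of entry.

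The wording could also mean five blocks rather than blocks of five. At 15 infants that is blocks of three, which are odd too.

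**Conclusion.** The point holds in limited form. That a block of five cannot balance two orders is certain on the natural reading, and nothing in the stated analysis compensates. The probability of 0.25 for a 9:6 split assumes 3:2 blocks of random direction. The plan does not state this; if the table were used without restriction, a batch of five would be 4:1 or 5:0 with probability 0.375.

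The size in events rests wholly on an assumed drift: below half an event at 9:6 for drifts up to 2.3, and 0.92 events, a fifth of the target effect, for a drift of 4.6. The consequence is bias in the estimate actually obtained and some lost power, not a false-positive problem. For larger drifts, much of the power loss comes from omitting period rather than from the split. The change is worth making because it costs almost nothing.

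**What to change.** 1. State the block size and composition. Replace the block of five with balanced even blocks, for example 2 and 4 in random order, on a list prepared in advance and concealed until the tube is in place. This guarantees 8:7 among 15 randomised infants; exact balance would need an even total, such as 14 or 16.
2. Prespecify period in the primary within-infant comparison. This also protects against an order split that shifts because an infant does not complete both recordings.
3. Keep the safety reports at every five infants, say whether they are cumulative, and show events by mode and period, since the first report cannot be balanced under any scheme.

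Cost: a few sentences and a new list before the first enrolment, with no added infants, visits or staff if the total stays at 15. The period term uses one degree of freedom. With no drift, simulated power falls from 0.949 to 0.946 at 8:7 and to 0.939 at 9:6.

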2. The subjects will be monitored continuously by: cardiorespiratory monitor, 2 pulse oximeters and by direct observation by study personnel during the set-up phase and each four hour observations. If, during the first trial, the event number or severity increases beyond what would be considered safe in normal clinical care, the mode will be considered a failure. The clinical team will be informed and the clinical team (not the investigators) will decide if, in their judgment, the alternate mode should be used for the second trial. If the increased event number or severity occurs during the second trial, the mode will be considered a failure, the clinical team will be informed and the clinical team will determine further care decisions.
3. The events are ones that are monitored as part of the usual care, and this will continue during the study period. These babies are always connected to monitors which are linked to nursing phones as well as central telemetry. The investigator doing the study will be present to assess/intervene, and as back-up, the clinical team will provide their routine care for such events.

3. If the disclosure of any of the information obtained during the study would place the individual at risk for harm (legal, reputation, emotional etc.) and the information will be recorded so that the individual could be identified, explain the protections that will be put in place to decrease the risk of disclosure:

Not applicable

4. \* The Code of Virginia requires that most medical personnel and all employees of institutions of higher education report suspected child/elder abuse or neglect. Is it likely investigators could discover information that would require mandatory reporting by the investigators or staff:

Yes  
 No

5. \* Is it likely investigators could discover a participant's previously unknown condition (eg disease, suicidal thoughts, wrong paternity) or if a participant is engaging in illegal activities:

Yes  
 No

6. If yes, explain how and when such a discovery will be handled:

7. \* Describe any potential risks or harms to a community or a specific population based on study findings:

None anticipated

8. \* Describe criteria for withdrawing an individual participant from the study; such as safety or toxicity concerns, emotional distress, inability to comply with the protocol, etc.:

If, between consent and study, the subject no longer meets inclusion criteria or does not meet exclusion criteria.

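### Apnea is scored by absence of airflow, but the plan does not say whether machine breaths count as airflow, so the apnea count could depend on the mode through the scoring rule alone

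*Combined protocol and SAP*

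**What the plan says.** **Scoring rule.** Research Description, item 4 (Analysis), scores apnea from the recordings as "cessation of breath resulting in no airflow for > 20 seconds or for > 5 seconds if accompanied by bradycardia" or desaturation. It names no recording and does not mention machine breaths. The lay wording in item 2 is "cessation of breath/low heart rate/low blood oxygen level events".

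**Outcome.** The primary outcome in item 4 reads: "The number of isolated apneas, bradycardias and desaturations and the number of combined events will be compared by mode of ventilation".

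**How the modes differ.** Item 4 (Subjects) says that on NIPPV "the ventilator sends a breath to match the prescribed rate like one every 3 seconds for a rate of 20 breaths per minute", whatever the infant's own breathing is doing. On NAVA the catheter detects diaphragm activity and "this mark of the beginning of inhalation is used to trigger a machine breath". The change of mode is made "at the same PEEP and respiratory rate". The plan does not explain what the rate means under NAVA, or what the ventilator does there when the diaphragm signal stops.

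**What is recorded.** In the item 4 data list, the only airflow-type measure is the ventilator's expired tidal volume. Data Confidentiality and Storage, item 1, adds an apnea monitor. Its output goes to the laptop with the ventilator data, is analysed for events, and yields the number and duration of apneas. What the monitor senses is not stated.

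**Bedside monitoring.** Risks, Discomforts, Potential Harms and Benefits, item 2, lists "cardiorespiratory monitor, 2 pulse oximeters and by direct observation by study personnel during the set-up phase and each four hour observations". The clinician is separately told of "events that cause alarms such as apnea or bradycardia or desaturations outside the clinical limits". Neither is named as the source for research scoring.

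**The concern.** The modes differ in when the machine delivers gas, and apnea is defined by gas not moving. Unless the plan says how machine breaths are treated, the definition can interact with the treatment being compared.

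Suppose an infant on NIPPV stops breathing with an open airway. Timed breaths continue, and a scorer working from ventilator flow or expired volume sees no qualifying gap. On NAVA as described, no effort means no triggered breath, so the same pause leaves a gap.

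Under that scoring, a NIPPV apnea would be handled as follows:

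- With bradycardia or desaturation lasting more than 5 s, it is recorded without its apnea component. If only one of the two is present, it becomes an isolated event.
- With bradycardia or desaturation lasting 5 s or less, it is not recorded at all. Only the apnea rule accepts an accompanying event with no minimum duration.
- Longer than 20 s with neither, it is lost.

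Both the apnea count and the isolated/combined split are at stake. Because the effect follows the mode, neither randomizing the order nor enrolling more infants removes it.

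**Working it through.** **Inputs.** The limits of >20 s and >5 s come from the Analysis text of item 4. The example rate of 20 per minute, with one breath every 3 s, comes from the Subjects text of item 4. The other rates below are my illustrations; the plan gives no range of NIPPV rates.

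**Step 1: the plan's own figure.** Interval T = 60 / rate = 60 / 20 = 3 s. This matches the plan.

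**Step 2: longest flow-free gap.** T runs from the start of one breath to the start of the next, so a gap without machine flow is at most T. A limit L can be met only if T > L.

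- For L = 5 s: 60 / rate > 5 requires a rate below 12 per minute.
- For L = 20 s: 60 / rate > 20 requires a rate below 3 per minute.

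**Step 3: fewest machine breaths inside a pause just longer than L**, which is L / T rounded down.

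| NIPPV rate (per min) | T (s) | Breaths in a pause >5 s | Breaths in a pause >20 s | >5 s limit reachable | >20 s limit reachable |
|---|---|---|---|---|---|
| 20 | 3 | 1 | 6 | no | no |
| 12 | 5 | 1 | 4 | no | no |
| 10 | 6 | 0 | 3 | yes | no |
| 3 | 20 | 0 | 1 | yes | no |

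At 12 per minute or more, neither limit can be reached from ventilator flow or expired volume with an open airway. The time taken by the machine breath shortens the gap further, so 12 per minute is a sufficient threshold, not an exact one.

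**Step 4: NAVA as described.** With no diaphragm signal there is no triggered breath, so a cessation of 25 s leaves a 25 s gap and is scored. If a rate is also set in NAVA, Steps 2 and 3 apply there too, and airflow scoring could miss unobstructed apneas in both modes.

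**Step 5: what the result depends on.** It needs three conditions: the airflow criterion is read from a ventilator signal, the airway is open, and each timed breath registers as flow. An obstructed pause on NIPPV could still be scored, and item 3 names loss of upper-airway opening as one mechanism of apnea.

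**The case against.** There are four serious counter-arguments.

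1. **Cessation of breath most naturally means the infant's own breathing.** I agree that this is the more natural reading. But the same sentence also requires that no airflow results. That clause can fail through machine breaths while the infant is apneic, and nothing tells the scorer to disregard them.

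2. **An apnea monitor is recorded and analysed for events.** This stands, and it narrows the gap. A reader might infer that the trial records no usable apnea signal; the data-storage section does not support that. What remains open is what the monitor senses, whether it separates infant from machine breaths, and which recording governs when they disagree.

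3. **NAVA may carry a set rate.** The wording on the switch allows it. If so, the asymmetry shrinks, but the need for a rule does not.

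4. **The literal airflow reading may be intended.** A pause ventilated by the machine would then not be an event, and part of the difference between modes would be treatment effect. That is a coherent definition, and the plan's background does say that NIPPV delivers machine breaths and reduces apneic events. It would have to be stated, because the count would then answer a different question from how often the infant stops breathing.

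A reader might also infer that the primary comparison is biased against NAVA by a known amount, or that power falls by a calculable figure. The documents support neither. They do not give the share of events that are apneas, and the 9.2 events per 4 hours under Study Population, item 3, is for all monitored events. Components could also move in opposite directions: under airflow scoring, apneas on NIPPV fall while isolated bradycardias or desaturations rise.

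**Conclusion.** The concern holds as a conditional point and should be fixed before scoring. The plan leaves open whether machine breaths count as airflow and which recording decides. On the literal reading, NIPPV at 12 per minute or more cannot yield a scorable unobstructed apnea, while NAVA as described can. This affects the apnea count and the isolated/combined split of the primary outcome.

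The arithmetic is exact. The consequence rests on the three conditions in Step 5 and on NAVA delivering no breath without effort, which no section confirms. The size and direction of any effect on the comparison cannot be derived. Bradycardia and desaturation keep their own thresholds, and their detection does not change.

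**What to change.** Amend the apnea definition in Research Description, item 4, for research scoring only and before any recording is scored. A later choice could be made knowing its effect on the comparison.

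1. Define apnea as cessation of the infant's own effective breathing, keeping the >20 s and >5 s limits.
2. State that machine breaths not triggered by the infant do not end an apnea in either mode. On NIPPV as described these are all the timed breaths; on NAVA, any machine breath without a preceding diaphragm signal.
3. Use the catheter's diaphragm signal, recorded in both 4-hour periods, to identify absent effort, and add it to the data list.
4. Keep pauses with continuing effort but no infant-generated airflow in the primary apnea count, whether obstructed or mixed, and also tabulate them by type. Count a continuous mixed pause once: 12 s without effort plus 12 s obstructed is 24 s and meets the >20 s limit, which neither part does alone.
5. Apply the same rule in both periods, and list unclassifiable pauses by mode.
6. State what the apnea monitor senses and its role in scoring.

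Bradycardia and desaturation scoring stay as they are.

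**Cost.** The infant undergoes no added procedure. Those on NIPPV already receive the NAVA catheter before randomization, and the planned count of wasted efforts in each mode already needs an effort signal in both. That implies, but does not confirm, that the waveform can be exported during NIPPV, so this should be checked first. The waveform must be stored, scoring takes somewhat longer, and classifying obstructed pauses is uncertain when an effort coincides with a timed breath.
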